8.3 Study procedures

There are no invasive procedures in this study. The procedures that all subjects will undergo are also listed under STUDY DESIGN.

8.4 Withdrawal of individual subjects

Subjects can leave the study at any time for any reason if they wish to do so without any consequences. The investigator can decide to withdraw a subject from the study for urgent medical reasons.

8.5 Replacement of individual subjects after withdrawal

Our goal is to investigate two groups of 24 patients (tremor-dominant vs. nontremor Parkinson's disease). We count on 6 dropouts per group based on bad eye tracking data, and up to 10 additional dropouts in the tremor-dominant group due to our strict inclusion criteria (ECG and measurement of blood pressure). We will therefore include at maximum 40 tremor-dominant and 30 non-tremor patients.

8.6 Follow-up of subjects withdrawn from treatment

Not applicable.

9. SAFETY REPORTING

9.1 Section 10 WMO event

In accordance to section 10, subsection 1, of the WMO, the investigator will inform the subjects and the reviewing accredited METC if anything occurs, on the basis of which it appears that the disadvantages of participation may be significantly greater than was foreseen in the research proposal. The study will be suspended pending further review by the accredited METC, except insofar as suspension would jeopardise the subjects' health. The investigator will take care that all subjects are kept informed.

9.2 AEs, SAEs and SUSARs

9.2.1Adverse events (AEs)

Adverse events are defined as any undesirable experience occurring to a subject during the study, whether or not considered related to [the investigational product / the experimental intervention]. All adverse events reported spontaneously by the subject or observed by the investigator or his staff will be recorded.

9.2.2Serious adverse events (SAEs)

A serious adverse event is any untoward medical occurrence or effect that at any dose:

- results in death;
- is life threatening (at the time of the event);
- requires hospitalisation or prolongation of existing inpatients' hospitalisation;
- results in persistent or significant disability or incapacity;
- is a congenital anomaly or birth defect;
- Any other important medical event that may not result in death, be life threatening, or require hospitalization, may be considered a serious adverse experience when, based upon appropriate medical judgement, the event may jeopardize the subject or may require an intervention to prevent one of the outcomes listed above.

The sponsor will report the SAEs through the web portal *ToetsingOnline* to the accredited METC that approved the protocol, within 15 days after the sponsor has first knowledge of the serious adverse events. SAEs that result in death or are life threatening should be reported expedited. The expedited reporting will occur not later than 7 days after the responsible investigator has first knowledge of the adverse event. This is for a preliminary report with another 8 days for completion of the report.

9.2.3Suspected unexpected serious adverse reactions (SUSARs)

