3. STUDY DESIGN

Interventions

I will manipulate the noradrenergic system using a 2x2 factorial design with factors PHARMACOLOGY (propranolol 40mg vs. placebo) and BEHAVIOR (stress induction vs. control) (Fig3). The two medication conditions (propranolol versus placebo) will be tested on two different days, to avoid carry-over effects. The two behavioural conditions (stress versus control) will be measured on the same day, in a block-wise manner, as shown in Fig 2. The order of the two medication conditions will be counter-balanced. Physiological markers of stress will be monitored throughout the scanning procedure (see below).

Pharmacological suppression of noradrenergic neurotransmission will be achieved using propranolol (40mg, oral dose). This is a non-selective β -adrenergic receptor-blocking agent that competes with β -adrenergic receptor stimulating agents at β 1- and β 2-adrenergic receptor sites. In healthy subjects, propranolol suppresses noradrenergic neurotransmission and functional connectivity within a cerebral salience network⁹. In Parkinson patients, there is mixed evidence regarding the anti-tremor effect of propranolol¹³⁻¹⁵, probably because in most cases contextual factors (stressful vs. neutral) were not taken into account³⁴. Peak plasma concentrations are reached 1 to 2 hours after administration, and remain stable for several hours^{35,36}. Therefore, in line with previous studies⁹, I will administer propranolol (or placebo) 105 min prior to fMRI scanning.

Behavioural noradrenergic stress induction will be achieved using a task that is wellvalidated task by our group, the cognitive co-activation task. This task involves alternating blocks of mental arithmetic versus rest. The dynamics of this task (rapid increases and decreases of both tremor and pupil diameter) make it possible to compare stress and rest conditions within a single fMRI session.

Measurements:

- ECG (on the first visit of the patient, prior to placebo/propranolol).

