Hypothesis 2: I will use correlations between pupil diameter and brain activity³⁹ to test for session-specific differences in the locus coeruleus-noradrenaline system. Pupil diameter is correlated with cerebral activity in the locus coeruleus³⁹, and is regarded as a reliable marker of noradrenergic activity^{42,43}. We have in-house experience with this method (collaboration with [name]). Nuclear imaging (PET) is less suitable for localizing the locus coeruleus-noradrenaline system: well-validated radioligands for the cerebral noradrenaline transporter are lacking, and the limited spatial resolution of PET prevents reliable measurements in the locus coeruleus ^{44,45}. I will also compare the structural integrity of the locus coeruleus, assessed using neuromelanin MR-scanning⁴⁰, between patients and controls.

Hypothesis 3: I will correlate patient-specific tremor-related patterns (#1) with noradrenergic measures (#2), and clinical tremor scores, to predict individual tremor characteristics based on the integrity of the locus coeruleus-noradrenaline system.

[figure not shown]

Fig4: design of the study. Placebo and Propranolol sessions will be counter-balanced.

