9.4 Follow-up of adverse events

All AEs will be followed until they have abated, or until a stable situation has been reached. Depending on the event, follow up may require additional tests or medical procedures as indicated, and/or referral to the general physician or a medical specialist. SAEs need to be reported till end of study within the Netherlands, as defined in the protocol.

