12.5 End of study report

The investigator will notify the accredited METC of the end of the study within a period of 8 weeks. The end of the study is defined as the last patient's last visit.

In case the study is ended prematurely, the investigator will notify the accredited METC within 15 days, including the reasons for the premature termination.

Within one year after the end of the study, the investigator/sponsor will submit a final study report with the results of the study, including any publications/abstracts of the study, to the accredited METC.

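### Adverse events are collected passively and no contact is described after the final session, so late reactions to about half the propranolol doses are captured only if the patient volunteers them

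*Protocol*

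**What the plan says.** Section 9.2.1 gives the scope, "Adverse events are defined as any undesirable experience occurring to a subject during the study", and the method of collection: "All adverse events reported spontaneously by the subject or observed by the investigator or his staff will be recorded". Section 9.4 covers events once they are known, "All AEs will be followed until they have abated, or until a stable situation has been reached", and sets the SAE period: "SAEs need to be reported till end of study within the Netherlands, as defined in the protocol". Section 12.5 supplies the end date: "The end of the study is defined as the last patient's last visit".

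On design, section 3 states under Fig. 4: "Placebo and Propranolol sessions will be counter-balanced". It places dosing 105 minutes before scanning, and says that plasma levels peak 1 to 2 hours after the dose and "remain stable for several hours". The Summary says blood pressure and heart rate are monitored during the measurements. Section 8.6, on follow-up of subjects withdrawn from treatment, is marked not applicable. No section describes a question put to patients about adverse events, or a contact after a session.

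**The concern.** The chance to learn of a late reaction depends on the order of treatment. A patient who takes propranolol in session 1 comes back for session 2 and meets staff again. That meeting prompts a report even though no question is scripted. A patient who takes it in session 2, or who is withdrawn after a propranolol dose in session 1, has no later meeting. For these patients a reaction that starts after they leave reaches the record only if they contact the team themselves.

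Some of the effects the protocol expects could plausibly first be noticed at home. The Summary lists dizziness and bradycardia, and section 11.4 lists nausea and orthostatic hypotension. What is at stake is the completeness of the safety record for the investigational product. For the last patient there is also the question whether a serious event later on the dosing day still falls within the reporting period.

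**Working it through.** The protocol states no figure for safety collection, so there is none to reproduce. The check is a count and a comparison of time windows.

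**1. Propranolol doses given at the patient's final session**

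Inputs: at most 40 tremor-dominant patients with one propranolol dose each (section 4.1); a target of 24 and up to 10 drop-outs from the ECG and blood-pressure criteria (section 8.5); counter-balanced order (section 3). The 30 non-tremor patients receive no drug.

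Formula: final-session doses = patients dosed × 1/2.

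| Patients dosed | Final-session propranolol doses |
|---|---|
| 40 (nobody lost before dosing) | 40 × 1/2 = 20 |
| 30 (all 10 ECG or blood-pressure drop-outs lost before dosing: 40 − 10) | 30 × 1/2 = 15 |
| 24 (target group only) | 24 × 1/2 = 12 |

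The row of 24 is a floor. Section 8.5 also allows for 6 losses per group from poor eye-tracking data, and those patients could already have been dosed.

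**2. Patients whose SAE window closes on the day of dosing**

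Sections 9.4 and 12.5 together give one study-wide date, not a date for each patient. Every patient who finishes before that date remains inside the window after the final session. Only the study's last patient can have no window left, so the count is at most 1:

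- of all doses: 1/40 = 2.5%, or 1/24 = 4.2%;
- of final-session doses: 1/20 = 5%, or 1/12 = 8.3%.

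The count is 0 if the last patient is in the non-tremor group or takes placebo last.

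**3. Observation after the dose**

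Inputs: 105 minutes from dose to scan (section 3) and about 60 minutes in the scanner (section 11.4).

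105 + 60 = 165 minutes = 2.75 hours.

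This covers the stated peak at 1 to 2 hours. It need not cover the several hours of stable levels that follow. Sessions last 4 to 5 hours by the Summary and 4 hours by section 11.4, so the true time on site after dosing may be longer. The session timeline (Fig. 4) is not shown, so the overlap cannot be fixed more closely.

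**4. Reactions missed**

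The protocol gives no rate of late reactions, so the number missed cannot be calculated. The counts in step 1 are patients for whom capture depends on their own initiative, not events lost.

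**The case against.** The strongest reply is that the protocol does have a working rule. Spontaneous reports and staff observations are recorded, known events are followed to resolution or stability, and blood pressure and heart rate are watched during the measurements. The study gives one dose of a long-used drug, and section 13 classes it as negligible risk. Safety is not an endpoint in section 8.1 and section 10 plans no comparison of adverse events, so uneven detection by order biases no stated analysis. The absence of later contact is inferred from silence. Consent pages were removed before review and may tell patients whom to call. All of this stands, and it keeps the severity low. It does not supply an active question or a scheduled contact.

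Three stronger readings are tempting, and the document does not support them:

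- **That reactions after the final session are not collected.** A volunteered event during the study is recorded, and SAEs stay reportable for every patient but the last until the study-wide end date.
- **That section 8.6 contradicts section 9.4.** Section 8.6 concerns follow-up of subjects withdrawn from treatment. Section 9.4 requires all known events to be followed and makes no exception for withdrawn subjects. The two can be read together, although neither provides a way to learn of a new event in someone withdrawn after dosing.
- **That the trial fails to support its statement in section 11.4 that side effects are reversible.** That is a prospective risk statement, set beside an appeal to existing clinical experience. It is not a conclusion planned from these data.

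**Conclusion.** The point holds as a weakness in safety collection. Late reactions to propranolol given in session 2 rest on the patient's initiative in about half of those dosed, roughly 12 to 20 patients. Propranolol-first patients have a return visit as a second opportunity. The SAE window after dosing can be zero for at most one patient, and possibly for none.

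This assumes that counter-balancing is close to 1:1 among those actually dosed, and that no contact is arranged in material not shown. Severity is low: no efficacy estimate or test changes. The case for acting is that the present method is weak and the improvement costs little.

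**What to change.** - **Section 9.2.1:** keep the recording of spontaneous and observed events. Add one scripted open question before the patient leaves each session and one short contact after each session, identical for placebo and propranolol. The investigators should set the timing of the contact and justify it against the plasma course described in section 3.
- **Section 8.6:** provide the same contact for anyone withdrawn after dosing.
- **Section 9.4:** keep the study-wide SAE window. Closing it for each subject at the contact would shorten the current window for most patients.
- **Section 12.5:** define end of study as the last subject's last contact, so that the window after dosing is never zero.

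Cost: at most 40 × 2 = 80 short calls by existing staff, fewer if patients drop out before dosing. End of study, and the reporting deadlines that run from it, move by about a day. No dose, session or analysis changes.

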9.3 Annual safety report

Not applicable.

9.4 Follow-up of adverse events

All AEs will be followed until they have abated, or until a stable situation has been reached. Depending on the event, follow up may require additional tests or medical procedures as indicated, and/or referral to the general physician or a medical specialist. SAEs need to be reported till end of study within the Netherlands, as defined in the protocol.

9.5 Data Safety Monitoring Board (DSMB)

10. STATISTICAL ANALYSIS

The data will be presented quantitatively.

10.1 Primary study parameter(s)

Functional MRI data will be pre-processed and analyzed with SPM12 (Statistical parametric mapping). As outlined above (STUDY DESIGN), we will test for tremor-related cerebral activity and functional connectivity as a function of TASK (stress vs. control) and PHARMACOLOGY (Propranolol vs. placebo). This gives rise to four activation images per subject (one for each condition), which will be entered into a 2 x 2 repeated measures ANOVA in SPM12. We will test for effects in pre-defined regions of interest, i.e. brain areas showing where we previously observed tremor-related activity (the basal ganglia, the brain stem, and the cerebello-thalamo-cortical circuit^{3,25}).

10.2Secondary study parameter(s)

- Locus coeruleus structural integrity. We quantify structural integrity of the locus coeruleus by comparing signal intensity (on the neuromelanin-sensitive MRI scan) between tremor-dominant and non-tremor Parkinson patients in an independent sample t-test, as done before ⁴⁹. Locus coeruleus signal intensity will be normalized with respect to the surrounding brain stem intensity.
- Clinical scores. Clinical tremor severity will be compared between the two sessions using paired t-tests. Non-tremor clinical scores will be compared between the two groups (tremor-dominant vs non-tremor) using t-tests.

10.30ther study parameters

Not applicable.

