4. STUDY POPULATION

4.1 Population (base)

Patients with idiopathic PD will be included through their neurologists at the Neurology department of the Radboud University Nijmegen Medical Centre, and through ParkinsonNext (see below). Nijmegen has a very large outpatient movement disorders clinic, and based on previous studies we expect no problems in recruiting enough patients for this research.

Number of subjects:

The full experiment, including testing on two different days, will be performed in 40 idiopathic Parkinson's disease patients with a tremor-dominant phenotype, defined as a resting tremor score of \geq 2 UPDRS points for at least one arm^{3,25}. This number of subjects gives reliable and replicable (validated across multiple cohorts) tremor-related activity^{3,25,31}. Since my focus is to understand how different experimental factors modulate cerebral and clinical correlates of resting tremor, I will use a within-patients (cross-over) design.

In addition, I will perform a subset of measurements in 30 non-tremulous Parkinson patients. These patients will only receive structural MRI scanning, resting state fMRI, and task-based fMRI on one day, to localize structurally and functionally localize the locus coeruleusnoradrenaline system. This group will not receive any intervention (behavioral or pharmacological). I will compare the structural and functional integrity of the locus coeruleus between tremor-dominant and non-tremor Parkinson patients.

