8.1.3 Other study parameters (if applicable)

The response of non-tremor PD symptoms (such as bradykinesia and rigidity), as well as age and gender, will be used as covariates in the analyses, despite careful matching of the two groups on these parameters. We will also quantify the effect of the intervention (Propranolol) on clinical tremor severity (rating scales).

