8.2 Randomisation, blinding and treatment allocation

Not applicable.

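### Neither cross-over analysis adjusts for visit, so any difference between the two days costs precision in the propranolol contrast, and biases it if completers per order are unequal

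*Protocol*

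**What the plan says.** Protocol Section 4.1 describes the tremor-dominant part as a cross-over: "I will use a within-patients (cross-over) design". Under Section 3 (Interventions), the two drug conditions "will be tested on two different days, to avoid carry-over effects", while stress and rest blocks alternate within each day. On order, the same section says "The order of the two medication conditions will be counter-balanced". Section 8.2, the place for randomisation and allocation, is marked not applicable.

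Section 10.1 tests tremor-related activity and connectivity "as a function of TASK (stress vs. control) and PHARMACOLOGY (Propranolol vs. placebo". The four images per patient are those "which will be entered into a 2 x 2 repeated measures ANOVA in SPM12". Section 10.2 adds: "Clinical tremor severity will be compared between the two sessions using paired t-tests". Section 8.1.3 says that the response of non-tremor symptoms, "as well as age and gender, will be used as covariates in the analyses". Visit, period, order and sequence appear in none of these analyses.

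**The concern.** Propranolol versus placebo is wholly a between-day comparison, so whatever differs between a first and a second visit is mixed into it. The outcome is tremor under a stress task that is repeated in the same scanner at the second visit, so some change between visits is plausible. Separate days deal with carry-over, not with a visit effect. Counter-balancing stops a visit effect from shifting the average drug contrast as long as the orders are equal among the patients analysed. It does not take the visit effect out of the error term.

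At stake are the precision of the drug contrast in a group of about 24 and, if the orders end up unequal, a shift in its estimate.

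**Working it through.** **The plan's own figures.** Section 4.4 expects 23–24 analysable tremor-dominant patients. 40 × 0.68 × 0.83 = 22.6, slightly below that but close enough to use n = 24. Section 8.5 agrees: 24 + 6 + 10 = 40. The protocol states no power, alpha, effect size or SD, so there is no power figure to reproduce.

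**Assumptions, not in the documents.** Two-sided alpha 0.05; true drug effect τ = 0.6; visit effect π from 0 to 1. Both effects are in units of the SD of the within-patient difference.

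**Model.** For patient i the propranolol-minus-placebo difference is d_i = τ + s_i·π + e_i. Here s_i = +1 if propranolol is given first and −1 if second, π is visit 1 minus visit 2, and SD(e) = 1. With n1 and n2 completers per order and n = n1 + n2:

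- Without a visit term: bias = π(n1 − n2)/n, and SE = √{[1 + π²(1 − ((n1 − n2)/n)²)·n/(n − 1)]/n}.
- With a visit term: the estimate is the unweighted mean of the two order-specific means, bias = 0, SE = ½√(1/n1 + 1/n2), and df = n − 2.

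**Balanced orders, 12/12.** At π = 0.5, SE without the term = √[(1 + 0.25 × 24/23)/24] = 0.229. With the term it is ½√(1/12 + 1/12) = 0.204, so the ratio is 1.12. Rejection rates are from simulation:

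| Visit effect (SD) | Power without term | Power with term |
|---|---|---|
| 0 | 80% | 80% |
| 0.25 | 79% | 80% |
| 0.5 | 73% | 80% |
| 0.8 | 61% | 80% |
| 1.0 | 50% | 80% |

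There is no bias here. The unadjusted test is conservative: its type I error is 2.9% at π = 0.5 and 0.6% at π = 1.0.

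**Unequal orders, no visit term.**

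| Split | Bias | Bias at π = 0.5 | Type I error at π = 0.5 | Type I error at π = 1.0 |
|---|---|---|---|---|
| 14/10 | 4/24 = 0.17π | 0.08 SD | 4.0% | 2.4% |
| 16/8 | 8/24 = 0.33π | 0.17 SD | 8.5% | 12.7% |

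At 14/10 the inflated SE outweighs the bias. With the visit term, type I error is about 5% and bias is 0 at both splits.

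**How unequal might the orders be?** Suppose 20 patients are assigned to each order and each is retained at random with probability 0.68 × 0.83. Equal orders then occur with probability 0.13, a difference of four or more with probability 0.26, and the mean |n1 − n2|/n is 0.11 (95th percentile 0.29). If only eye-tracking losses follow assignment (14 per order, 83% retained), equal orders occur with probability 0.20 and the mean imbalance is 0.07.

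**Interaction.** Bias in the drug-by-task contrast = (π_stress − π_rest)(n1 − n2)/n. It is zero when the visit effect is the same in stress and rest blocks. With a visit effect of 0.5 SD in stress blocks only, it is 0.08 at 14/10 and 0.17 at 16/8.

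**The case against.** Several counter-arguments carry weight.

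- **No visit effect is documented.** The task validation described in Section 1 shows change between blocks, not between visits. If there is no visit effect, nothing is lost. This stands, and it is why the power figures run from zero.
- **Imbalance may be small.** Section 8.5 attributes up to 10 losses to ECG and blood pressure, and Section 4.4 moves ECG approval ahead of the sessions, so some losses may come before an order is assigned. The EMG-fMRI analysis in 10.1 uses no pupil data, so its n may be nearer 27 (40 × 0.68 = 27.2). This also stands: lost precision is the surer harm and bias the lesser one.
- **A SAP could add the term.** It could. But the protocol itself names the factors, the tests and the covariates. Two of the covariates, age and gender, cannot absorb a within-patient change between visits.

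Three stronger readings are tempting, but the documents do not support them.

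- A reader might infer that habituation will pass for a propranolol effect. It does so when propranolol comes second, but it masks the drug equally when propranolol comes first. With balanced orders the two cancel in the estimate, and at 14/10 type I error remains below 5%.
- A reader might infer that the answer to Objective 1 is generally biased. A visit effect common to stress and rest cancels from the interaction. The stress-amplification part of that objective rests on the within-day task contrast, where an additive visit effect also cancels because each completer contributes both visits.
- A reader might infer that the SPM model tests the drug effect against one pooled error term and is therefore too liberal. Section 10.1 specifies neither a single pooled error nor the absence of a non-sphericity correction.

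**Conclusion.** The point holds as a weakness in the stated analysis. Both cross-over analyses leave out the visit term, and the drug contrast is entirely between days. With 12/12 orders the consequence is lost power: none without a visit effect, about 1 percentage point at 0.25 SD, 7 at 0.5 SD and 19 at 0.8 SD. With unequal orders there is also a bias of π(n1 − n2)/n. That is modest at 14/10, and it raises type I error above 5% only at the more extreme 16/8 split (about 8% at 0.5 SD).

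The sizes rest on an assumed visit effect, an assumed true effect of 0.6 SD and n = 24. The direction of the argument does not. The interaction is touched only if stress reactivity itself changes between visits.

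**What to change.** - **Section 10.1:** adjust the drug and drug-by-task contrasts for visit. Either add a visit and a visit-by-task term, or carry each patient's drug and interaction contrast images to a second-level model with sequence as a between-subject factor, testing the unweighted mean over the two sequences. The task main effect needs no such term.
- **Section 10.2:** replace the paired t-test for clinical tremor with a two-period cross-over analysis, for example a mixed model with treatment and visit fixed and patient random.
- **Reporting:** give the number of completers per order.

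The cost is wording and one degree of freedom, with no new data and no added burden for patients. If there is no visit effect and the orders are unequal, a little precision is lost: at 14/10 with a true effect of 0.6 SD, power is 79% with the term against about 80% without it.

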dominant patients to arrive at ± 24 individuals with complete and high-quality data (40 x $68\% \times 83\% = 23-24$ subjects). Drop-out is much less for the non-tremor group, given that there is no intervention, and only one session. In sum, this means that we will measure at maximum 40 tremor-dominant and 30 non-tremor patients. To avoid more early drop-outs in the tremor-dominant group, we will take the following measures: during screening, we will prioritize patients who have also participated in the Personalized Parkinson's Project (PPP), since a recent ECG is available for these patients. Other patients will be asked whether an ECG has been made recently, if so we will give these patients priority. We will request recent ECGs and only after an MD has approved that it meets all inclusion criteria, patients will be invited to participate. Remaining patients with no ECG available are invited to come to the institute prior to the scheduled sessions, to make an ECG and make sure they can undergo the propranolol intervention. Finally, we will be stricter in selecting suitable patients during our phone screening, and we will not invite patients with a disease duration of >10 years, considerable ON/OFF fluctuations or daily levodopa-equivalent dose of >1200 mg. In addition, shortening the protocol by leaving out the threat-of-shock task will hopefully increase quality of eye-tracking data.

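### The locus coeruleus group comparison is fixed as an unadjusted t-test in section 10.2, while section 8.1.3 commits to covariates, one of them undefined in the non-tremor group

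*Protocol*

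**What the plan says.** Section 8.1.2 names locus coeruleus structural integrity, from neuromelanin-sensitive MRI, as the secondary endpoint. Section 10.2 gives its analysis: signal intensity, normalised to the surrounding brain stem, is compared "between tremor-dominant and non-tremor Parkinson patients in an independent sample t-test". No covariate is mentioned.

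Section 8.1.3 lists three covariates. The first is worded as a response of non-tremor symptoms, with bradykinesia and rigidity as examples; the others are age and gender. It says that these "will be used as covariates in the analyses, despite careful matching of the two groups on these parameters". Its next sentence turns to the drug: "We will also quantify the effect of the intervention (Propranolol) on clinical tremor severity".

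On the non-tremor group, section 4.1 says: "This group will not receive any intervention (behavioral or pharmacological". Section 4.4 explains the lower drop-out in that group as "given that there is no intervention, and only one session". Section 4.4 also says that the groups are matched for age, gender and non-tremor disease characteristics (duration and severity).

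Section 3, under the main analyses for Hypothesis 2, describes the same structural comparison as being "between patients and controls".

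**The concern.** Sections 8.1.3 and 10.2 are both written as firm commitments, and they cannot both describe the single analysis of this endpoint. An unadjusted and an adjusted comparison can give different estimates and different p-values. With both in the protocol, the choice between them could be made after the data are seen.

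The choice matters more here than in a randomised comparison. Phenotype is not assigned, so any remaining difference between the groups in age, gender or disease severity enters the unadjusted difference directly. The protocol evidently intends to guard against this, since it asks for covariates in spite of matching.

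The first covariate cannot be used as written. A response needs two conditions to compare, and section 8.1.3 does not say what the response is to. Patients with one session and no drug have no response to a drug.

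**Working it through.** **1. The two analyses side by side.**

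| | Section 10.2 | Section 8.1.3 |
|---|---|---|
| Comparison | Tremor-dominant versus non-tremor | Analyses involving the two matched groups |
| Method | Independent-sample t-test | Covariates used in the analyses |
| Covariates | None | Non-tremor symptom response, age, gender |

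The reference to matching of the two groups ties the covariate rule to between-group comparisons. Section 10.2 contains two: locus coeruleus signal and the non-tremor clinical scores. The second compares the groups on the scores themselves, so the symptom covariate has no role there. Within section 10.2 the rule therefore points at the locus coeruleus test.

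**2. The three covariates.** Age and gender exist in both groups. A response of non-tremor symptoms does not exist in a group with no intervention and one session. Severity does, and section 4.4 lists it among the matching variables. Because 8.1.3 says the groups are matched on these parameters, severity is the likelier meaning.

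**3. How many scans this endpoint has.** The plan's own figure comes first: 40 × 0.68 × 0.83 = 22.6, against a stated 23–24 (slightly lower, not material here). Section 8.5 adds up: 24 + 6 + 10 = 40 and 24 + 6 = 30.

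The 83% factor and the 6 losses per group concern eye tracking. The neuromelanin scan is done once and its signal needs no pupil data. For this endpoint:

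- tremor-dominant: 17/25 = 0.68, and 40 × 0.68 = 27.2, about 27;
- non-tremor: 19/19 usable so far, and 30 × 1 = 30.

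**4. Cost of adjustment.** Three covariates use three degrees of freedom:

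- 27 versus 30: residual df fall from 27 + 30 − 2 = 55 to 52;
- 24 versus 24: residual df fall from 24 + 24 − 2 = 46 to 43, and the two-sided 5% critical t rises from 2.013 to 2.017, about 0.2%.

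**5. Gain from adjustment.** The residual standard error is multiplied by √(1 − R²), where R² is the share of variance explained by the covariates. The protocol gives no R², so the range is an assumption.

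| R² | √(1 − R²) | Fall in standard error |
|---|---|---|
| 0.10 | 0.949 | 5% |
| 0.20 | 0.894 | 11% |
| 0.30 | 0.837 | 16% |

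This treats the covariates as nearly balanced between groups, which matching should bring about. Remaining imbalance would reduce the gain.

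**6. What that means for detectable differences.** Assume two-sided alpha 0.05, 80% power and 24 versus 24; alpha and power are not in the protocol. The noncentral t uses noncentrality d / [√(1 − R²) × √(1/24 + 1/24)]. The unadjusted t-test detects d = 0.83. With three covariates the detectable d is 0.83, 0.79 (0.785), 0.74 and 0.69 for R² of 0, 0.10, 0.20 and 0.30. Adjustment costs almost nothing if the covariates are useless and helps if they are not.

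**The case against.** The strongest reply is that this is a consistency slip on a secondary endpoint. The groups are matched on the same variables, which should bring the two analyses closer together, and full model detail can be left to a statistical analysis plan. Part of that stands: the consequence is moderate and a short clarification resolves it. But the protocol did not leave the matter open. It made two incompatible commitments, and it asked for covariates knowing that the groups were matched.

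Four stronger readings are tempting, and the protocol does not support them.

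- **Attrition destroys the matching.** A reader might combine drop-out with eye-tracking failure (40 × 0.68 × 0.825 = 22.4) and infer that the analysed groups are no longer matched. Eye-tracking failure does not remove a neuromelanin scan, and nothing shows that the remaining losses unbalance the groups. A chance-imbalance formula for independent samples would also ignore the matching.
- **The covariates can act nowhere else.** They could also serve the functional locus coeruleus comparison in section 4.1 and the between-patient correlations under Hypothesis 3 in section 3.
- **The symptom covariate is a post-treatment variable that absorbs part of the drug effect.** The sentence on propranolol that follows invites this reading, but 8.1.3 never says what the response is to, and the groups could not have been matched on a drug response.
- **A control group is missing.** The summary, the objectives and sections 4.1 and 10.2 all define two Parkinson groups. The wording in section 3 is loose and changes no analysis.

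**Conclusion.** The point holds as a conflict within the protocol: section 10.2 fixes an unadjusted test for the named secondary endpoint, section 8.1.3 commits to covariates, and the first covariate is undefined for one of the two groups as worded. It should be corrected, but it does not touch the primary endpoint.

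The textual conflict needs no assumption. The size of the benefit does: a 5–16% smaller standard error if the covariates explain 10–30% of the variance in locus coeruleus signal, and essentially no gain or loss in precision if they explain none. No direction or size of bias in the unadjusted difference can be derived from the document. The case for adjustment rests on the comparison being non-randomised and on the protocol's own stated intention. The reading of response as severity is an inference from the matching phrase, and the investigators should confirm it.

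**What to change.** **Section 10.2.** Make the primary analysis of locus coeruleus integrity a linear model of normalised signal on group, age, gender and one OFF-state non-tremor motor score (bradykinesia plus rigidity). Report the unadjusted t-test as supporting. The score must be available in both groups and unaffected by study drug: for tremor-dominant patients, taken before dosing or in the placebo session.

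**Section 8.1.3.** Replace the wording about the response of non-tremor symptoms with OFF-state severity of those symptoms.

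**Section 3, Hypothesis 2 (editorial).** Name the compared groups as tremor-dominant and non-tremor patients instead of patients and controls.

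**Cost.** About three degrees of freedom, with no extra patients. Age and gender need no new measurement, and section 3 already lists the MDS-UPDRS-III. Its timing relative to dosing is not stated in the text, so the investigators should confirm that a drug-free OFF-state score exists for every tremor-dominant patient before the wording is fixed.
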